## 6.2 Demographics

A by-subject listing of Baseline demographic characteristics will be presented by PS0016 randomized treatment group based on all subjects screened, ie ES. This will include the year of birth (if available), age (in years), sex, race, ethnicity, height (in cm), weight at PS0016 Screening (in kg) and BMI for all subjects enrolled into PS0018. The age will be directly entered into the study database and will not be re-calculated for the statistical analysis.

All Baseline demographic characteristics (with the exception of year of birth) will be summarized by PS0016 randomized treatment group and for all subjects based on the SS. The summary of age will include descriptive statistics and categorical summaries, the latter based on requirements for EudraCT and clinicaltrials.gov reporting.

The tabulation will be repeated for the FAS, only if the SS differs from the FAS.

## 6.3 Other Baseline characteristics

The following Baseline characteristics will be presented in a by-subject listing for the SS:

- \*Percentage BSA involvement
- \*PASI total score
- IGA score
- \*HADS-A and HADS-D scores

Baseline for each variable (where applicable) is defined in [Table 3–1](#).

The Baseline characteristics listed above will be summarized using descriptive statistics (for continuous variables only\*). The IGA score will be summarized including the number and percentage of subjects with each specific IGA score.

The tabulation will be presented by PS0016 randomized treatment group and for all subjects based on the FAS.

## 6.4 Medical history and concomitant diseases

Medical history not reported in PS0016 will be listed for the SS by PS0016 randomized treatment group. The reported term will be included in the listing as well as whether the condition is related to psoriasis (yes/no). A glossary of all medical history conditions will be presented for the SS including the system organ class (SOC), preferred term (PT) and reported term.

Concomitant medical procedures performed during the study will be listed for the SS.

## 6.5 Prior and concomitant medications

Prior and concomitant medications will be listed for the SS by PS0016 randomized treatment group and subject and summarized for the SS by WHODD Anatomical Main Group (Level 1), Pharmacological Subgroup (Level 3) and PT. Tabulations will be presented by PS0016 randomized treatment group and for all subjects, with separate tabulations for prior (and concomitant categories).

All tabulations will be sorted alphabetically by Level 1 term, alphabetical Level 3 term within Level 1 and decreasing frequency of PT in the 'All Subjects' column.

A glossary of all prior and concomitant medications will be presented for the SS including the Anatomical Main Group (Level 1), Pharmacological Subgroup (Level 3), PT and reported term.

### 6.5.1 Prior medication definition

Prior medications include any medications that started prior to the date of administration of the first dose of PS0018 study medication.

### 6.5.2 Concomitant medication definition

Concomitant medications are medications taken on or after the start of PS0018 study medication and up to and including 28 days after last dose, ie during the Open-Label Treatment Period.

Any medication that started prior to PS0018 dosing and continued after dosing will therefore be classified as both prior and concomitant. Such medications will therefore be counted in tabulations for both prior and concomitant categories.

Any medications with missing dates and/or times will be handled as described in [Section 4.2.4](#) in order to classify them as prior or concomitant.

## 7 MEASUREMENTS OF TREATMENT COMPLIANCE

During the Open-Label treatment period of this study, study medication will be administered in the clinic and compliance will be determined at the visit by study personnel.

Due to the method of administration of the treatments, compliance will be examined in terms of completed number of injections. One dose of 160 mg requires one injection, one dose adjustment of 320 mg requires two injections. A dose reduction from 320 mg back down to 160 mg is allowed.

Treatment compliance will be calculated as:

$$\text{Overall compliance (\%)} = \frac{\text{total number of completed injections}}{\text{total number of expected injections}} \times 100 \quad [6]$$

where the total number of expected injections is derived relative to when the subject finishes treatment. If a subject discontinues early, then the number of expected completed injections is based on the date of early discontinuation relative to the dosing visits. The planned dose recorded at a given visit will indicate if one injection for bimekizumab 160 mg Q4W, or two injections for bimekizumab 320mg Q4W are expected to be given. If a subject completes treatment with no dose adjustment, 12 injections are expected (one each at Weeks 0, 4, 8, 12, etc. through to Week 44).

The calculated overall compliance will be listed by PS0016 randomized treatment group and subject, and summarized by PS0016 randomized treatment group, based on the SS. The summary will include both descriptive statistics for overall compliance (n, mean, SD, median, minimum and maximum) and the number and percentage of subjects based on the following classifications:

- Compliance  $\leq$ 80.0%
- Compliance  $>$ 80.0%

## 8 EFFICACY ANALYSES

All efficacy listings will be based on the FAS and be summarized based on this population. Changes and improvements from Baseline are relative to PS0016 Baseline.

Supportive summaries based on observed case data will be included for all analysis based on imputations, see [Section 4.2](#).

### 8.1 Derivations of efficacy variables

#### 8.1.1 Psoriasis Area and Severity Index

The PASI is the most commonly used assessment for grading the severity of psoriasis in clinical studies and quantifies the severity and extent of the disease and weighs these with the percentage of BSA involvement. The body is divided into four regions comprising the head (h), upper extremities (ue), trunk (t), and lower extremities (le). In each of these regions, the total surface area of involvement (A) is graded on a scale of 0 to 6 (0 for no involvement up to 6 for 90% - 100% involvement). The body regions and associated BSA are presented in [Table 8–1](#).

**Table 8–1: Body regions for calculation of percent BSA for PASI**

Body region	Details of region	BSA	Area-of involvement of body region (A) a
Head (h)	Face, back of head	10%	0 to 6
Upper limbs (ue)	Left, right, upper lower, flexor surface, extensor surface	20%	0 to 6
Trunk (t)	Front, back, groin	30%	0 to 6
Lower limbs (le)	Left, right, upper lower, flexor surface, extensor surface, including buttocks	40%	0 to 6
Total		100%	

A=area of involvement score; BSA=body surface area; PASI=Psoriasis Area and Severity Index

a Where 0=none; 1=1% to <10% affected, 2=10% to <30% affected, 3=30% to <50% affected, 4=50% to <70% affected, 5=70% to <90% affected, 6=90% to 100% affected.

Scoring of psoriatic plaques for the PASI is based on 3 criteria: redness (R), thickness (T), and scaliness (S). Severity is rated for each index (R, T, S) on a scale of 0 to 4 (0=none, 1=slight, 2=moderate, 3=marked, and 4=very marked).

The various body regions are weighted to reflect their respective proportion of BSA. The composite PASI score is then calculated by multiplying the sum of the individual severity scores (R, T and S) for each region by the weighted area of involvement score (A) for that respective region, and then summing the 4 resulting quantities as follows:

$$\text{PASI} = 0.1 \times [(\text{Rh} + \text{Th} + \text{Sh}) \times \text{Ah}] + 0.2 \times [(\text{Rue} + \text{Tue} + \text{Sue}) \times \text{Aue}] + 0.3[(\text{Rt} + \text{Tt} + \text{St}) \times \text{At}] + 0.4 \times [(\text{Rle} + \text{Tle} + \text{Sle}) \times \text{Ale}] \quad [7]$$

The following rules will be applied in the calculation of the PASI score in case of missing data:

- If 1 or 2 severity measurements are missing for a certain region (eg head), the average of the remaining measurements within that region will be utilized to substitute the missing values
- If the area of affected skin and/or all severity measurements for 1 or 2 regions are missing, then the missing (R+T+S)×A for a region will be substituted by the average of the available (R+T+S)×A across the remaining regions
- If the PASI assessment has more missing data than indicated above, at a given visit, then the PASI will be set to missing for that visit

The highest potential PASI score is 72 for severe disease; the lowest score is 0 which indicates no psoriatic lesions are present. The PASI scores are considered as a continuous variable and will be calculated and presented to 1 decimal place in the listings. The percentage change in PASI score from PS0016 Baseline will be calculated as follows:

$$\text{Percentage change from PS0016 Baseline} = 100 \times [(\text{PS0018 PASI} - \text{PS0016 Baseline PASI}) / \text{PS0016 Baseline PASI}] \quad [8]$$

Thus, for subjects with an improvement in the PASI score, the percentage will be negative. For subjects with a worsening in the PASI score, the percentage will be positive.

A categorical response variable, such as PASI90, is defined to be equal to 1 if the percentage improvement from PS0016 Baseline in the PASI scores is 90% or greater and 0 if the percentage improvement from PS0016 Baseline is less than 90%. This definition is introduced for the purpose of identifying subjects who respond to the treatment (1 = responder, 0 = non-responder). Similarly, the categorical secondary efficacy variables PASI50, PASI75, and PASI100 response are equal to 1 for subjects with improvements of 50% or greater, 75% or greater and 100% from PS0016 Baseline in PASI score, respectively (and equal to 0 otherwise).

If a subject does not achieve PASI50 at Week 12 or reverts below PASI50 later during the PS0018 study based on a change from PS0016 Baseline then they will be withdrawn from the study.

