Furthermore, a supportive analysis specifically for adjusters will be performed in which PASI score will be summarized by visit, where Baseline is recalibrated for each individual subject and defined as the visit where the bimekizumab 320mg Q4W dose is initiated. The visits summarized

will be in weeks relative to when the bimekizumab 320mg Q4W dose was started as opposed to the scheduled week of the PS0018 assessment. These summaries will be based on observed data only.

The PASI50, PASI75, PASI90, and PASI100 responses are based on at least 50%, 75%, 90%, and 100% improvement from Baseline in the PASI score. Thus, the following will apply:

- If the percentage improvement is  $\geq 50\%$  then the subject is a PASI50 responder
- If the percentage improvement is  $\geq 75\%$  then the subject is a PASI75 responder (and is a PASI50 responder also)
- If the percentage improvement is  $\geq 90\%$  then the subject is a PASI90 responder (and is a PASI50 and PASI75 responder also)
- If the percentage improvement is 100% then the subject is a PASI100 responder (and is a PASI50, PASI75 and PASI90 responder also)

The number and percentage of subjects achieving a PASI50, PASI75, PASI90, and PASI100 response will be tabulated by visit and overall and by PS0016 randomized treatment group and by Dose adjustment. The 95% CI for the percentage of responders will be calculated using a Wilson approximation and be included in the tabulation.

In addition, the percentage of responders (including 95% CI) will be plotted at each PS0018 visit for each response variable. Separate plots will be presented for each of PASI50, PASI75, PASI90 and PASI100 with both treatment groups overlaid on the same plot. These plots will be presented by PS0016 randomized treatment and by Dose adjustment separately.

For the purpose of the tabulation the lower and upper 95% confidence limits for the percentage of responders will be truncated at 0 and 100% respectively.

Missing data will be imputed using NRI as described in [Section 4.2.1.1](#). Subjects with missing data will be regarded as non-responders for the PASI50, PASI75, PASI90, and PASI100 variables.

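### The PASI missing-data rule in SAP 8.1.1 has no exception for an area score of 0, so a clear region whose severity items are left blank is treated as unknown instead of as zero

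*SAP*

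**What the plan says.** SAP 8.1.1 grades area in each of four regions as "0 for no involvement up to 6 for 90% - 100% involvement". Of the plaque characteristics it says "Severity is rated for each index (R, T, S) on a scale of 0 to 4 (0=none, 1=slight", so a zero code exists for severity as well. Equation [7] multiplies the severity sum by the area score in each region and adds the four products with weights 0.1, 0.2, 0.3 and 0.4. Of the total, the SAP says "the lowest score is 0 which indicates no psoriatic lesions are present".

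Three missing-data rules follow:

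- One or two missing severity items within a region are replaced by the average of the items present in that region.
- The second rule applies "If the area of affected skin and/or all severity measurements for 1 or 2 regions are missing". The product "for a region will be substituted by the average of the available" products in the remaining regions.
- With more missing than that, "then the PASI will be set to missing for that visit".

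For the responder tables, SAP 8.2.1 adds: "Subjects with missing data will be regarded as non-responders for the PASI50, PASI75, PASI90, and PASI100 variables". SAP 4.2.1.1 sends missing items to the 8.1.1 rules and carries the last total score forward (LOCF) in the continuous summaries. Protocol 12.1 describes the scoring but has no rule for missing items. Neither document says how severity is recorded when the area score is 0.

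**The concern.** When the area score is 0, the regional product is 0 whatever the severity fields contain. Nothing is unknown, so nothing needs imputing. The and/or in the second rule nevertheless lets blank severity alone trigger substitution, and no sentence exempts area 0.

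An assessor who records no involvement in a region may see no lesion to rate and leave redness, thickness and scaliness blank. If so, the rule acts most on subjects with the most clear regions, who are the best responders. The error also has one direction: the substitute is a mean of non-negative products put in place of a true 0, so it can leave the PASI unchanged or raise it, never lower it. At stake are the PASI75, PASI90 and PASI100 proportions and the continuous PASI summaries.

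**Working it through.** **Inputs.** The weights, scales and missing-data rules are from SAP 8.1.1, NRI is from SAP 8.2.1, and the planned maximum of 45 subjects is from SAP 2.4. Blank severity in clear regions and all baseline PASI values below are assumptions.

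**The plan's own figure.** With area 6 and severity 4+4+4 everywhere, each product is 12 × 6 = 72. The weights sum to 1, so PASI = 72. With zeros everywhere PASI = 0. The stated range of 0 to 72 reproduces.

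**First rule.** It does no harm when area is 0, because any imputed severity is multiplied by 0.

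**Second rule, two clear regions.** Head and upper limbs have area 0 with severity blank; trunk and lower limbs have product 4 each.

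- True PASI: 0.3×4 + 0.4×4 = 2.8.
- Substitute: (4+4)/2 = 4.
- Literal rule: 0.1×4 + 0.2×4 + 2.8 = 4.0.

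PASI90 requires a score of at most 0.10 × baseline. The true score qualifies from 2.8/0.10 = 28 and the literal score from 4.0/0.10 = 40, so PASI90 is lost for baselines from 28 to below 40. PASI75 requires at most 0.25 × baseline: 2.8/0.25 = 11.2 and 4.0/0.25 = 16, so it is lost from 11.2 to below 16.

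| Assumed baseline | True improvement | Literal rule | Change |
|---|---|---|---|
| 15 | 1 − 2.8/15 = 81.3% | 1 − 4.0/15 = 73.3% | PASI75 lost |
| 28 | 1 − 2.8/28 = 90.0% | 1 − 4.0/28 = 85.7% | PASI90 lost |

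**A second pattern.** Head and trunk are clear and blank; upper and lower limbs have product 3 each. True PASI is 0.2×3 + 0.4×3 = 1.8; the literal rule gives 3.0. At baseline 20, improvement is 91% true against 85% literal, and PASI90 is lost. At baselines 12, 15 and 30 the pairs are 85%/75%, 88%/80% and 94%/90%, and no PASI75 or PASI90 status changes. The effect on responder status depends on the case.

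**General inflation when the remaining products are equal.** The ratio is 1/(1 − weight of the blank clear regions). For one region it runs from 1/0.9 = 1.11 to 1/0.6 = 1.67. For two regions it runs from 1/0.7 = 1.43 to 1/0.3 = 3.33.

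**Mixed recording.** Head and trunk are clear and blank, upper limbs are clear and scored 0/0/0, and lower limbs have product 3. The substitute is (0+3)/2 = 1.5. The literal PASI is 0.1×1.5 + 0.3×1.5 + 0.4×3 = 1.8, against a true 1.2. The mean includes clear regions that were scored, so the inflation is smaller.

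**Third rule.** With three blank clear regions and lower limbs at product 3, the true PASI is 0.4×3 = 1.2 but the literal result is missing. With four blank clear regions the true PASI is 0 and the literal result is again missing. Both are NRI non-responders. Each fully clear subject recorded this way costs 1/45 = 2.2 percentage points of PASI100 if 45 are analysed. If all four regions are scored 0/0/0, or two are blank and two scored 0/0/0, the literal rule still gives PASI 0 and PASI100 is met.

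**The case against.** The strongest reply is that the triggering data pattern is not shown to occur. Both documents give severity a code for none, and Protocol 12.1 asks for the three ratings in each body area. The SAP expects a clear subject to receive a computed score of 0. A clear region scored 0/0/0 triggers no missing-data rule. This stands, and it makes the point conditional.

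Second, the second rule replaces a product described as missing, and a programmer could hold that a product with area 0 is known and so not missing. That is a fair reading, but the trigger clause points the other way. Two defensible programs could assign different responder status to the same subject.

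Third, safeguards exist: electronic PASI records (Protocol 13.2.1), cleaning checks (Protocol 13.3.2) and the data evaluation meeting before lock (SAP 3.4). They might expose the pattern, but none states the convention.

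Fourth, non-responder status is confined to the NRI tables, and IGA (SAP 8.2.3) is unaffected. That is correct, but the other PASI summaries do not restore the true value. The observed-case percentages drop a subject whose PASI is missing, and LOCF carries forward a score that may predate clearance.

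A reader might infer that clear regions always take the average of diseased regions, that every fully clear subject becomes a non-responder, or that the response rates are biased. The documents support none of these. The substitute averages all remaining regions, including clear ones scored 0; loss of the score needs at least three blank regions; and blank recording is not established.

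**Conclusion.** The gap in the text is real: SAP 8.1.1 covers the case of area present with all severity missing, makes no exception for area 0, and so replaces a known zero. Its effect is conditional on clear regions being left blank. In that event the PASI can only be overstated, by 1.11 to 1.67 times with one such region and 1.43 to 3.33 times with two when the other products are equal. With three or four the score is lost. Changes in responder status depend on baselines that the documents do not give, and the ranges shown are illustrations. PASI is summarised descriptively in a study whose primary objective is safety, so this is a small clarification worth making because it costs almost nothing. It is not evidence of bias in the results.

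**What to change.** Insert in SAP 8.1.1, ahead of the missing-data rules: *If A for a region is 0, (R+T+S)×A is 0 regardless of the severity fields. Regional substitution applies only when A is missing, or when A>0 and all severity scores are missing. Only such regions count toward the limit of two.* Confirm from the eCRF or the electronic PASI specification whether severity is scored 0, filled automatically or left blank when area is 0.

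With this rule, four blank clear regions give PASI 0, three blank clear regions with lower limbs at product 3 give 1.2, and the head-and-upper-limbs example gives 2.8. The cost is one sentence and one line of code. If zeros are already recorded for clear regions, no result changes.

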### 8.1.2 Investigator's Global Assessment Response

A static IGA for psoriasis will be used to assess disease severity in all subjects during the study. The Investigator will assess the severity of psoriasis using a 5-point scale [Table 8–2](#).

A clinical response with regard to the IGA is defined as Clear (0) or Almost Clear (1) with at least a 2 category improvement from PS0016 Baseline on a 5-point scale.

**Table 8–2: Investigator's Global Assessment**

Score	Short Descriptor	Detailed Descriptor
0	Clear	No signs of psoriasis; post-inflammatory hyperpigmentation may be present
1	Almost clear	No thickening; normal to pink coloration; no to minimal focal scaling
2	Mild	Just detectable to mild thickening; pink to light red coloration; predominately fine scaling
3	Moderate	Clearly distinguishable to moderate thickening; dull to bright red, clearly distinguishable to moderate thickening; moderate scaling
4	Severe	Severe thickening with hard edges; bright to deep dark red coloration; severe/coarse scaling covering almost all or all lesions

For the handling of missing data see [Section 4.2.1.3](#).

### 8.1.3 Hospital Anxiety and Depression Scale

The scores for each item range from 0 to 3, with higher scores indicating more severe anxiety or depression [Table 8–3](#). The total score for each domain ranges from 0 to 21. A score of <8 for a given domain is considered as normal.

In case of missing individual data, the following rules will be applied:

- If a maximum of 1 item is missing in a given domain, the missing item will be imputed with the mean score from the remaining completed items within the same domain
- If more than 1 item is missing in a given domain, the domain subscore will not be calculated

For the handling of missing domain data see [Section 4.2.1.4](#).

## 8.2 Statistical analysis of the primary efficacy variables

In addition to the summaries described below, the impact of dose adjustment on efficacy will be considered. This will be done primarily by using descriptive statistics to summarize PASI score for each visit by PS0016 randomized treatment group and the dose adjustment categories as defined in [Section 4.10](#) along with the All Subjects (ie All BKZ) group. This will be based on observed data only.

### 8.2.1 Psoriasis Area and Severity Index

The individual scores for the PASI for each body region (redness, thickness and scaliness severity scores and area of involvement score [A]), and the derived total PASI score (from 0 to 72) will be listed for each subject by PS0016 randomized treatment group and visit. The listing will include the change from PS0016 Baseline and percentage change from Baseline for the total score only. Subjects achieving a PASI50, PASI75, PASI90 and PASI100 response at each visit will be flagged in the listing. Missing data will not be imputed for the listings.

Descriptive statistics (including 95% CI) will be presented by PS0016 randomized treatment group and overall and by Dose adjustment, and by visit for absolute values, changes from PS0016 Baseline and percentage change from PS0016 Baseline (based on the total PASI score only). For the purpose of the tabulations the lower and upper 95% confidence limits will be truncated as follows:

- For the absolute values the lower 95% confidence limit will be truncated at 0 and the upper 95% confidence limit will be truncated at 72
- For the changes from Baseline the lower 95% confidence limit will be truncated at -72 and the upper 95% confidence limit will be truncated at +72
- For the percentage change from Baseline the lower 95% confidence limit will be truncated at -100%, there will be no truncation of the upper 95% confidence limit

The following figures will be presented:

- Combined individual (spaghetti) plots displaying percentage change from Baseline in PASI score versus time (visit) by PS0016 randomized treatment group (all subjects will be overlaid on the same plot with separate plots for each PS0016 randomized treatment group)
- Mean (with 95% CI) percentage change from Baseline in PASI score versus time (visit) by PS0016 randomized treatment group (both treatment groups will be overlaid on the same plot)

All tabulations and both individual and mean figures will be presented using the FAS with imputation and observed cases. All listings will be presented using the SS.

For subjects that discontinue the study, missing data will be imputed using LOCF as described in [Section 4.2](#) for the tabulations and mean figures.

Missing data will not be imputed for the individual figures.

Furthermore, a supportive analysis specifically for adjusters will be performed in which PASI score will be summarized by visit, where Baseline is recalibrated for each individual subject and defined as the visit where the bimekizumab 320mg Q4W dose is initiated. The visits summarized

will be in weeks relative to when the bimekizumab 320mg Q4W dose was started as opposed to the scheduled week of the PS0018 assessment. These summaries will be based on observed data only.

The PASI50, PASI75, PASI90, and PASI100 responses are based on at least 50%, 75%, 90%, and 100% improvement from Baseline in the PASI score. Thus, the following will apply:

- If the percentage improvement is  $\geq 50\%$  then the subject is a PASI50 responder
- If the percentage improvement is  $\geq 75\%$  then the subject is a PASI75 responder (and is a PASI50 responder also)
- If the percentage improvement is  $\geq 90\%$  then the subject is a PASI90 responder (and is a PASI50 and PASI75 responder also)
- If the percentage improvement is 100% then the subject is a PASI100 responder (and is a PASI50, PASI75 and PASI90 responder also)

The number and percentage of subjects achieving a PASI50, PASI75, PASI90, and PASI100 response will be tabulated by visit and overall and by PS0016 randomized treatment group and by Dose adjustment. The 95% CI for the percentage of responders will be calculated using a Wilson approximation and be included in the tabulation.

In addition, the percentage of responders (including 95% CI) will be plotted at each PS0018 visit for each response variable. Separate plots will be presented for each of PASI50, PASI75, PASI90 and PASI100 with both treatment groups overlaid on the same plot. These plots will be presented by PS0016 randomized treatment and by Dose adjustment separately.

For the purpose of the tabulation the lower and upper 95% confidence limits for the percentage of responders will be truncated at 0 and 100% respectively.

Missing data will be imputed using NRI as described in [Section 4.2.1.1](#). Subjects with missing data will be regarded as non-responders for the PASI50, PASI75, PASI90, and PASI100 variables.

The tabulation will also be repeated using observed cases for both treatment assignments that will include a category for missing data. Those who discontinue will be counted in the missing category for this tabulation where applicable. For this tabulation based on observed cases, the denominator for the percentage of responders and non-responders, will be the number of subjects with nonmissing data at the visit.

